#### **4.2.3 Progression Free Survival**

PFS is defined for each subject as the time between randomization date and the date of progression or death, whichever occurs first. The date of progression will be taken from the investigator assessment of progression on the CRF. A subject who dies without reported prior progression will be considered to have progressed on the date of death if no subsequent therapy prior to death date. For those who remain alive and have not progressed, PFS will be censored on the date of last evaluable tumor assessment (TA) prior to subsequent therapy. For those who remain alive and have no recorded evaluable TAs post baseline, PFS will be censored on the date of randomization.

For subjects without baseline tumor assessment, PFS will also be censored on the date of randomization.

Modified variables will be examined for the purposes of sensitivity analysis:

- *PFS accounting for early TAs in DTIC group* is defined in the same manner as PFS, except that for subjects randomized to DTIC with radiographic, photographic or clinical evidence of progression before Week 12, subjects will be considered to have PD at Week 12.

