#### **4.2.6 Duration of Response**

Primary duration of response (DoR) definition for the randomized subjects whose BOR is CR or PR is defined as the time between the date of response of CR or PR (whichever occurs first) and the first date of progressive disease (PD) or the date of death (whichever occurs first).

Per protocol DoR definition for the response evaluable subjects whose BOR is CR or PR is defined as the time between the date of response of CR or PR (whichever occurs first) and the first date of progressive disease (PD) or the date of death (whichever occurs first).

For both definitions, for subjects who underwent tumor resection following response but prior to disease progression, DoR will be censored on the date of the last evaluable TA prior to resection. For subjects who remain alive and have not progressed following response, DoR will be censored on the date of last evaluable TA prior to subsequent therapy.

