#### **4.2.7 Duration of Stable Disease**

Primary duration of stable disease (DoSD) definition for the randomized subjects whose BOR is SD is defined as the time between the randomization date and the first date of PD or the date of death (whichever occurs first).

Per protocol DoSD definition for the response evaluable subjects whose BOR is SD is defined as the time between the randomization date and the first date of PD or the date of death (whichever occurs first).

For both definitions, for subjects who underwent tumor resection following SD but prior to disease progression, DoSD will be censored on the date of the last evaluable TA prior to resection. For subjects who remain alive and have not progressed following SD, DoSD will be censored on the date of last evaluable TA prior to subsequent therapy.

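### DoR and DoSD count a death after subsequent therapy as an event but censor a surviving switcher before the switch; this disagrees with the PFS death condition, which itself lacks a censoring date

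*SAP*

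**What the plan says.** **PFS (SAP 4.2.3).** The opening sentence reads "PFS is defined for each subject as the time between randomization date and the date of progression or death, whichever occurs first". A later sentence narrows this: a subject who dies with no progression reported "will be considered to have progressed on the date of death if no subsequent therapy prior to death date". On censoring, "For those who remain alive and have not progressed, PFS will be censored on the date of last evaluable tumor assessment (TA", taking the last one before any subsequent therapy. Living subjects with no evaluable post-baseline scan go to the randomization date. One rule ignores vital status: "For subjects without baseline tumor assessment, PFS will also be censored on the date of randomization".

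**DoR (SAP 4.2.6).** The endpoint is "the first date of progressive disease (PD) or the date of death (whichever occurs first", with no condition on therapy. Censoring before a switch applies to subjects "who remain alive and have not progressed following response, DoR will be censored on the date of last evaluable TA prior to subsequent therapy". For resection before progression, "DoR will be censored on the date of the last evaluable TA prior to resection", whether or not the subject later dies.

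**DoSD (SAP 4.2.7).** This is "the time between the randomization date and the first date of PD or the date of death (whichever occurs first", with the same two censoring rules as DoR.

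**Elsewhere.** SAP Section 8 says that all subjects enter the Kaplan-Meier analyses, censored where appropriate, but gives no date for this case. It allows further conventions in the Data Presentation Plan. Protocol 5.4.9 stops best overall response at progression or subsequent therapy, whichever is earlier. Protocol 5.4.10 ends both durations at progression and does not mention death. SAP 7.5 makes the PFS p-value descriptive, and SAP 3.2 only estimates DoR and DoSD per arm.

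**The concern.** Take two responders who start a new therapy on the same day, neither with progression reported nor resected. Their histories are identical at that point. Under SAP 4.2.6 the one who survives is censored before the new therapy, and the one who dies a year later is at risk throughout and counts as an event. A Kaplan-Meier risk set should depend only on what is known at each time; here it depends on what happens afterwards. Of these switchers, the only ones left at risk after the switch are those already certain to have an event.

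PFS has a related but smaller gap. The SAP withholds event status from such a death and then does not say where to censor the subject. Two programmers could choose different dates. For a subject whose best response is stable disease, PFS and DoSD share the same start and the same nominal end, yet they treat the same death differently.

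**Working it through.** The plan states no figure for PFS, DoR or DoSD, so there is nothing to reproduce. The check is a comparison of the rules, followed by date arithmetic.

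**1. The rules side by side**, for a subject with a baseline scan who starts subsequent therapy with no reported progression and no resection:

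| Later status | PFS (4.2.3) | DoR (4.2.6) | DoSD (4.2.7) |
|---|---|---|---|
| Alive | Censored, last evaluable scan before therapy | Same | Same |
| Dead | Not an event under the condition; no date | Event at death | Event at death |

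There are two exceptions. Without a baseline scan, PFS is censored at randomization. With resection before progression, DoR and DoSD are censored before resection even if the subject dies.

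**2. Size of the rule difference for given dates.** SAP Section 8 gives duration = later date − earlier date + 1, and 30.4375 days per month. Protocol 5.4.2 puts induction scans at Weeks 12, 18 and 24. With Week n = Day 7(n − 1) + 1, these are Days 78, 120 and 162; Days 78 and 162 match Protocol Table 5.1-1. Assumed: randomization on Day 1, last scan Day 120, new therapy Day 130, death (if it occurs) Day 420.

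- DoR, response at Day 78. Alive: 120 − 78 + 1 = 43 days (1.4 months), censored. Dead: 420 − 78 + 1 = 343 days (11.3 months), event.
- DoSD, best response stable disease. Alive: 120 − 1 + 1 = 120 days (3.9 months), censored. Dead: 420 − 1 + 1 = 420 days (13.8 months), event.
- PFS for the subject who dies. No event and no stated date under the condition; 120 days if the living-subject rule is borrowed; an event at 420 days if the opening sentence is read alone.

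The gap is always death day minus last-scan day, here 420 − 120 = 300 days (9.9 months). Other assumed dates give other gaps: 200 − 162 = 38 days (1.2 months), or 730 − 78 = 652 days (21.4 months). These are examples and not bounds.

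**3. Direction.** Keeping a dying switcher at risk raises the curve until the death, which then lowers it. The net effect on a median cannot be signed from the documents.

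**4. A hypothetical PFS hazard ratio.** The documents give no switch rates. A simulation assumed 120 versus 60 patients, median time to progression 3 months in both arms (true HR 1), median 6 months from progression to death, and every pre-progression switcher dying with no progression reported. Each setting had 200 runs, so the Monte Carlo error of the mean log HR is about √(1/120 + 1/60)/√200 = 0.011.

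| Switching, ipilimumab / DTIC | HR, event at death | HR, censored at last scan |
|---|---|---|
| 5% / 5% | 0.99 | 0.99 |
| 10% / 10% | 1.02 | 1.01 |
| 5% / 15% | 1.15 | 1.04 |
| 5% / 25% | 1.33 | 1.11 |

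The choice matters here only when switching differs by arm. Censoring is not neutral either: switch times were drawn as a fraction of each patient's own time to progression, so the censoring is informative by construction.

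**5. Does the protocol resolve it?** The version supplied is Revised Protocol 04, whose Sections 8.3 and 8.4.1 are marked not applicable. SAP 2.0 reflects Revised Protocol 03 (SAP Table 2.4-1 and Section 10). The retained text of Protocol 5.4.10 does not mention death.

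**The case against.** A reader might infer that SAP 4.2.3 contradicts itself and leaves PFS undefined. The text does not support that. A specific condition normally qualifies a general opening definition, and reading the opening sentence alone would empty the condition of meaning. The only date that section links to subsequent therapy is the last evaluable scan before it. The PFS defect is therefore a missing clause with an evident completion.

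A reader might also infer that the protocol never settled the point. That cannot be said, because Revised Protocol 03 and the Data Presentation Plan were not available. Either may hold a convention, although it would not remove the written difference between SAP 4.2.3 and SAP 4.2.6 and 4.2.7.

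Third, DoSD need not be PFS restricted to stable disease: DoSD has a resection rule and PFS has none. That stands, so a difference between the two endpoints is not an error in itself. It does not excuse a rule that turns on later vital status.

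Fourth, counting every death as an event would also make the three endpoints agree. It would, but it would override the SAP's own PFS condition and still leave surviving switchers censored before the switch.

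Finally, no result is shown to move. That also stands, and it limits the weight of the point.

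**Conclusion.** The point holds for DoR and DoSD as written: whether time after a switch counts depends on whether the patient later dies, and the treatment of that death disagrees with the SAP's own PFS condition. For PFS, the death is on the natural reading not an event, and a censoring date is missing for subjects with a baseline scan.

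The consequence is limited. PFS is a secondary endpoint with a descriptive p-value, and DoR and DoSD are estimates per arm. The documents do not support any inference that the primary 2-year survival rate is affected, or that a reported median or hazard ratio is biased by a known amount. The number of patients concerned is unknown, and every day count and hazard ratio above rests on assumed inputs. The correction is worth making because it is cheap and the present DoR and DoSD rule goes wrong when followed exactly.

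**What to change.** 1. **SAP 4.2.6 and 4.2.7.** Apply the PFS condition: death is an event only if no subsequent therapy began before it. Subjects without reported progression who started subsequent therapy are censored at the last evaluable scan before that therapy, whatever their later vital status. The resection rule stays. No randomization fallback is needed, because best overall response is taken only up to subsequent therapy (Protocol 5.4.9).
2. **SAP 4.2.3.** Extend the existing censoring sentence to subjects who die after subsequent therapy without reported progression. Where no evaluable post-baseline scan precedes that therapy, censor at randomization, worded identically for living and dead subjects.
3. **Scope.** State that progression first reported after subsequent therapy is not addressed. Such progression can still count as an event, so dependence on the future is reduced but not removed, unless the same cut-off is applied to progression in all three endpoints.

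The database lock for these endpoints was 03Jun2019 (Protocol 5.4.2). The DoR and DoSD change alters a stated rule, so document it as a post-lock rule change and report both endpoints under the SAP 2.0 wording alongside.

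The cost is a few sentences and a second set of DoR and DoSD summaries, with no new data. There may be fewer events, and censoring at a switch may be informative in an open-label trial.

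Separately, SAP Section 8 describes DoR as for confirmed responses, while SAP 4.2.6, SAP 7.5.7 and Protocol 5.4.8.2 require no confirmation. That is an editorial slip to correct on its own.

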#### **5.4.9 Best Overall Response**

The best overall response is determined once all the data for the subject is known. It is defined as the best response designation, as determined by the investigator, recorded between the date of randomization and the date of objectively documented progression per RECIST v1.1 or the date of subsequent therapy, whichever occurs first. For subjects without documented progression or subsequent therapy, all available response designations will contribute to the BOR assessment. The subject's best overall response assignment will depend on the findings of both target and non-target disease and will also take into consideration the appearance of new lesions.

For purposes of this study, the minimum scan time from baseline for determination of SD will be 8 weeks.

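### SAP 4.2.3 limits PFS deaths and censoring by subsequent therapy but not progressions, so a subject who switches before progression is handled by later outcome, and the secondary PFS hazard ratio can shift if switching differs by arm

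*SAP*

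**What the plan says.** SAP 4.2.3 builds PFS from four statements.

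- Definition: "PFS is defined for each subject as the time between randomization date and the date of progression or death, whichever occurs first".
- Source of the progression date: "The date of progression will be taken from the investigator assessment of progression on the CRF". Subsequent therapy is not mentioned.
- Death without reported progression: the subject is "considered to have progressed on the date of death if no subsequent therapy prior to death date".
- Subjects alive without progression: "PFS will be censored on the date of last evaluable tumor assessment (TA) prior to subsequent therapy".

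For duration of response, SAP 4.2.6 uses the same censoring idea for subjects alive without progression: "DoR will be censored on the date of last evaluable TA prior to subsequent therapy". SAP 4.2.7 does likewise for duration of stable disease. Both sections count death as an event with no subsequent-therapy condition.

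For best overall response, protocol 5.4.9 closes the window at the "date of objectively documented progression per RECIST v1.1 or the date of subsequent therapy, whichever occurs first".

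Comparing PFS between arms is a secondary objective (SAP 3.2). It is analysed with a stratified log-rank test and a stratified Cox hazard ratio with an 80% CI (SAP 7.5.3). SAP 7.5 calls the PFS p-value descriptive.

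**The concern.** Subsequent therapy restricts two of the three possible outcomes (death and censoring) but not the third (progression). What happens to a switcher therefore depends on events after the switch. A switcher who later progresses keeps the post-switch time and contributes an event. One who does not is withdrawn retroactively from the risk set at a scan before the switch. Censoring chosen by a future outcome is informative, and it carries the effect of the next therapy into PFS for only some switchers.

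The trial is open-label, so switching before progression could differ by arm. The PFS hazard ratio could then depart from 1 with no treatment effect on progression. A reader could not tell the direction without knowing which arm switched more, how long scans continued and how active the next therapy was.

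**Working it through.** **1. The rule applied to three subjects.** All are progression-free at the Week 12 and Week 18 scans and start another therapy before Week 24.

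| Outcome after the switch | Handling under SAP 4.2.3 |
|---|---|
| Progression at Week 24 | Event at Week 24 |
| Alive, no progression | Censored at Week 18 |
| Dies without progression | Not an event (death clause); not covered by the censoring clause, which is for those who remain alive; no date given |

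The histories are identical up to the switch. SAP section 8 expects every subject to contribute to the PFS curve, so the third subject needs a date that 4.2.3 does not supply.

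**2. Does other text close the gap?** No.
- SAP 7.1 excludes only assessments in re-induction and the progression follow-up after it.
- Protocol 5.4.9 governs best overall response only.
- SAP 7.5.3 and 7.5.3.1 add no rule. The one modified PFS variable concerns early assessments in the DTIC arm.

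**3. The plan's own figure.** No power or event count is stated for PFS. The only power figure is 80% for 2-year survival (SAP section 5: 120 vs 60, 25% vs 12.5%, two-sided alpha 0.20).
- SE = sqrt(0.25×0.75/120 + 0.125×0.875/60) = 0.0582.
- z = 0.125/0.0582 = 2.148; power = Φ(2.148 − 1.282) = 80.7%.

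The figure reproduces, and the PFS rule does not enter it.

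**4. Size, with switching unrelated to prognosis.** The true hazard ratio is 1.00.

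First set of inputs, 600 simulated trials per scenario. From SAP section 5: 120:60 subjects, 18-month accrual, 42-month cut-off. Assumed:
- PFS median 3 months in both arms;
- switching before progression in 10-20% on ipilimumab and 20-40% on DTIC;
- post-switch median 3 or 6 months, with 0 or 30% durable control;
- post-switch scans for 6 months or to cut-off.

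Results: the rule as written gives a mean hazard ratio of 0.91-1.11; censoring every switcher at the switch gives 0.98-1.01.

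Second set, large-sample. Assumed:
- progression median 4 months and death median 30 months;
- scans at Weeks 12, 18 and 24 (protocol 5.4.2), then every 12 weeks;
- next therapy multiplies the progression hazard by 1, 0.5 or 0.25.

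Selected rows:

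| Switching, ipilimumab vs DTIC | Post-switch scans | Hazard multiplier | As written | All switchers censored | Switch ignored |
|---|---|---|---|---|---|
| 11% vs 33% | 6 months | 1 | 0.92 | 0.99 | 1.00 |
| 11% vs 33% | never stop | 0.25 | 1.08 | 0.99 | 1.17 |
| 33% vs 11% | 6 months | 1 | 1.09 | 1.01 | 1.00 |
| 33% vs 11% | never stop | 0.25 | 0.93 | 1.01 | 0.86 |
| 22% vs 45% | 6 months | 1 | 0.91 | 0.98 | 0.99 |
| 22% vs 45% | never stop | 0.25 | 1.09 | 0.99 | 1.16 |

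With short post-switch scanning, early progressors count and the rest vanish from the risk set, which inflates the hazard in the arm that switches more. With long scanning and an active next therapy, added progression-free time lowers that hazard instead. Equal switching (22% each) gave 1.00 under every rule. A further run on other inputs, also with independent switching, spanned about 0.87-1.24 as written and about 1.00 with uniform censoring, so the size depends on the inputs.

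**5. Size, with switching driven by impending progression.** Assumed: true hazard ratio 1.00, median 3 months, switch at 60-100% of the time to progression.

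| Switching, ipilimumab vs DTIC | As written | All switchers censored |
|---|---|---|
| 10% vs 30% | 1.00-1.03 | 1.23 |
| 15% vs 40% | 1.00-1.04 | 1.34 |

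A separate run at the same switching rates gave 1.00-1.23 as written and 1.22-1.36 with uniform censoring.

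**6. Set against precision.** With d PFS events split 2:1, SE(log HR) = sqrt(4.5/d). For an assumed d of 120 to 170, SE is 0.194 to 0.163, and the 80% half-width (1.282 × SE) is 0.248 to 0.209. Since ln 0.91 = −0.094 and ln 1.11 = 0.104, the extreme shifts of the first set are 0.094/0.248 = 38% to 0.104/0.209 = 50% of the half-width.

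**The case against.** Four objections have force.

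- **The rule is inferred from silence.** No sentence says that a progression after subsequent therapy counts. The death clause, the censoring clause and the response window all suggest that subsequent therapy was meant as a cut-off. SAP section 8 leaves further conventions to a Data Presentation Plan that is not available here. This stands: it may be a drafting omission. It does not remove the need to state the rule, because a programmer following 4.2.3 as written would count those progressions.
- **Post-switch progressions may rarely have been recorded.** The current protocol no longer carries the follow-up schedule of the randomized phase, and the documents do not settle whether scans continued after a switch. This limits what can be said about size.
- **Uniform censoring is not shown to be less biased.** A reader might infer from step 4 that it removes the bias. That result rests on switching being unrelated to prognosis; step 5 reverses the ranking. The documents support neither mechanism. The case for one rule is coherence with the SAP's own clauses, and the analysis ignoring subsequent therapy must stand beside it.
- **Duration of response and of stable disease are not the same case.** A reader might extend the hazard-ratio argument to them. SAP 7.5.7 and 7.5.8 give per-arm estimates only, so there is no ratio to distort, and their death rule differs from that of PFS.

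Different windows for best overall response and PFS are also not an error in themselves; the response window only shows which convention the trial already uses.

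**Conclusion.** The inconsistency is in the current text: subsequent therapy limits deaths and censoring but not progressions, and a switcher who dies without progression has no assigned outcome. If switching before progression differs by arm, the secondary PFS hazard ratio can shift to about 0.91-1.11 when the truth is 1.00. This rests on the first set of assumed inputs and on switching unrelated to prognosis. With equal switching and a true ratio of 1.00 there is no shift.

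A reader might infer that the trial's PFS result is biased, or that its main conclusion is at risk. The documents support neither: they give no switching rates, the PFS p-value is descriptive, and the primary 2-year survival comparison does not use this rule. The change is worth making because it is specific and cheap, and because the direction of any distortion cannot be judged from the reported hazard ratio.

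**What to change.** In SAP 4.2.3, apply one rule to every subject who starts subsequent anti-cancer therapy. Count progression or death as an event only if dated on or before the start of that therapy. Otherwise censor at the last evaluable tumor assessment on or before that start, whatever happens later; if there is none after baseline, censor at randomization, as 4.2.3 already does for subjects alive with no such assessment.

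Beside it, report a PFS analysis that ignores subsequent therapy for everyone, and the number of subjects in each arm who switched before progression. The two analyses answer different questions, since the second includes the effect of the next therapy. Their difference and the counts show how much the choice matters.

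In SAP 4.2.6 and 4.2.7, align the event and censoring rules in the same way, including for deaths.

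Cost: SAP wording, one derivation and one extra table. Dates of subsequent therapy are already to be listed (SAP 7.4.6). There will be slightly fewer PFS events and slightly wider 80% CIs. The protocol gives 03Jun2019 as the database lock, so a change made after that date should be labelled post hoc and shown beside the result under the present wording.

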#### **4.2.4 Disease Control Rate**

Primary disease control rate (DCR) definition is defined as the number of subjects in the arm with Best Overall Response (BOR) of complete response (CR), partial response (PR), or stable disease (SD), divided by the total number of randomized subjects in the arm.

Per protocol DCR definition is defined as the number of response evaluable subjects in the arm with BOR of complete response (CR), partial response (PR), or stable disease (SD), divided by the total number of response evaluable subjects in the arm.

